#### **Background and Aim**

This statistical analysis plan concerns the long-term follow-up (4-2.5 years after baseline assessment) of the VIA Family trial. We conducted the VIA Family trial in Denmark between 2017-2020. The trial aimed to test for superiority of the VIA Family intervention compared with treatment as usual (TAU) in improving children's, parents' and families' functioning and wellbeing. Eligible families had at least one parent with a lifetime severe mental illness diagnosis (SMI) (i.e. recurrent moderate to severe depression, bipolar disorder, or schizophrenia spectrum disorder), at least one child between the age of 6-12 years, and lived within the municipalities of Frederiksberg or Copenhagen (Denmark). The trial had a randomized, two-armed, parallel and controlled design. The participating families were randomly allocated to both groups with an allocation ratio of 1:1. For more information see study protocol.

We invited families for the 4-year follow-up assessment who at baseline had been randomized to one of the two treatment arms. Families who had withdrawn their consent for participation or had requested not to be

contacted for future follow-up were not invited for participation. At 4-year follow-up we invited only one parent to participate to represent the primary informant of the child.

The aim of the 4-year follow-up was to study potential long-term effects of the VIA Family intervention.

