and sex (registered at birth) as fixed effects and a random effect of family to address non-independence among siblings within the same family.

Changes in parent- and family-specific outcomes (FAD, PSP, PSS) including allocation group, baseline measurement, and parental diagnosis as covariates.

Mean differences in change between the VIA Family intervention and TAU groups, along with a 95% confidence interval, will be reported with corresponding p-values.

Model assumptions will be assessed using residual diagnostics. Severely skewed outcomes will be log-transformed prior to analysis.

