## Subgroup analyses

To explore whether the intervention's effects vary among different demographic or clinical subgroups, the primary analysis will be repeated within the following subgroups:

- a. Children without neurodevelopmental disorders (ASD, ADHD) compared with children with neurodevelopmental disorders at baseline and at end-of-intervention (1.5 years follow-up).
- b. Families with young children, i.e., 6-9 years at baseline compared with families with older children, i.e., 10-12 years at baseline.
- c. Families with low functioning at baseline (characterized by the 35% lowest combined scores in CGAS, HOME and PSP).
- d. Families where all family members (parents and all children) have been participating in at least the introductory sessions of VIA Family compared with families where not all family members participated.
- e. Families whose primary motivation to participate at baseline was to receive support compared with families whose primary motivation was to support a scientific project.

Estimated treatment differences from the subgroups will be reported in forest plots.

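### Subgroup d splits families by attendance at VIA Family sessions, which only the VIA arm can have, so on no reading are both of its forest-plot rows randomised VIA-versus-TAU differences

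*SAP*

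**What the plan says.** The SAP describes the trial in Background and Aim: "The trial had a randomized, two-armed, parallel and controlled design". VIA Family is the experimental arm and TAU the control.

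The section on primary and secondary analyses specifies, for SDQ, a linear mixed model with allocation group as a fixed effect. The reported quantity is "Mean differences in change between the VIA Family intervention and TAU groups", with a 95% confidence interval and p-value. The opening of Statistical Analyses places all analyses in the ITT population, whatever the adherence.

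Subgroup analyses gives its purpose as "To explore whether the intervention's effects vary among different demographic or clinical subgroups" and its method as "the primary analysis will be repeated within the following subgroups". It ends: "Estimated treatment differences from the subgroups will be reported in forest plots".

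Item d compares families in which all parents and children "have been participating in at least the introductory sessions of VIA Family compared with families where not all family members participated".

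Item a compares children without ASD or ADHD with children "with neurodevelopmental disorders at baseline and at end-of-intervention (1.5 years follow-up".

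**The concern.** A subgroup treatment effect keeps the protection of randomisation only if the same rule, applied to information that treatment cannot have changed, sorts families in both arms. Item d fails on both counts. It uses behaviour after randomisation, and that behaviour is attendance at the experimental treatment itself, so it has no counterpart in TAU.

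Its rows would nevertheless stand in the same forest plot as items b, c and e, which are defined at baseline. A reader would take all rows as comparable estimates of effect modification. If families who bring everyone to the introductory sessions differ in prognosis from those who do not, the two rows can differ when the intervention does nothing. The natural but unsupported reading would be that VIA Family works better when the whole family attends.

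**Working it through.** **What each row needs.** The primary analysis estimates an allocation effect, so each row needs families from both arms who are comparable apart from allocation. The SAP does not state outright that TAU families had no VIA Family sessions. That follows from the two-arm design, and nothing in the SAP suggests otherwise. The SAP has no rule for classifying TAU families under item d, no predicted attendance for TAU, and no complier-average or principal-stratum method. Three readings remain.

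1. *Literal.* No TAU family attended VIA Family sessions, so the full-attendance row has 0 TAU families and its allocation effect cannot be estimated. The incomplete-attendance row sets only the incompletely attending part of VIA against all of TAU.
2. *All TAU families in both rows.* Both rows can be computed, but each compares a self-selected part of VIA with unselected controls.
3. *VIA families only.* Allocation group is constant, so there is no VIA-minus-TAU difference to plot.

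None of these tests effect modification.

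**Illustration of size.** The SAP gives no attendance rate and no correlation between attendance and outcome, so every input here is assumed:

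- There is no true treatment effect.
- p is the share of VIA families meeting the rule, 0.5 to 0.8.
- Attendance is a standard normal latent score above c = Φ⁻¹(1 − p).
- k = r − ρa is the baseline-adjusted covariance between latent attendance and outcome, where r is the attendance–outcome correlation, a the attendance–baseline correlation and ρ the baseline–outcome correlation.
- k is taken as 0.1 or 0.2. For example, r = a = 0.4 and ρ = 0.5 give k = 0.4 − 0.5 × 0.4 = 0.20, a partial correlation of 0.20/√(0.75 × 0.84) = 0.25.

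Bias against all of TAU, in outcome SD:

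- full-attendance row: kφ(c)/p
- incomplete-attendance row: −kφ(c)/(1 − p)
- gap between rows: kφ(c)/[p(1 − p)]

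At p = 0.5 and k = 0.2, φ(0) = 0.399, so the rows are ±0.2 × 0.399/0.5 = ±0.160 and the gap is 0.319.

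| k | p | Full attendance | Incomplete attendance | Gap |
|---|---|---|---|---|
| 0.2 | 0.5 | 0.160 | −0.160 | 0.319 |
| 0.2 | 0.6 | 0.129 | −0.193 | 0.322 |
| 0.2 | 0.7 | 0.099 | −0.232 | 0.331 |
| 0.2 | 0.8 | 0.070 | −0.280 | 0.350 |
| 0.1 | 0.5 | 0.080 | −0.080 | 0.160 |
| 0.1 | 0.6 | 0.064 | −0.097 | 0.161 |
| 0.1 | 0.7 | 0.050 | −0.116 | 0.166 |
| 0.1 | 0.8 | 0.035 | −0.140 | 0.175 |

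Under reading 1 only the incomplete-attendance column applies. Under reading 2 all columns apply. Signs reverse for negative k, and every entry is 0 at k = 0.

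A simulated baseline-adjusted regression with 1,000,000 families per arm and k = 0.2 gave gaps of 0.327, 0.330, 0.338 and 0.354 for p = 0.5 to 0.8, within 0.01 of the formula.

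A second simulation, without baseline adjustment, let attendance correlate 0.7 with a family-resources factor that itself correlated 0.2 or 0.4 with SDQ change (lower is better), with 50% or 70% attending. With no true effect, fully attending families showed differences of −0.07 to −0.22 SD (false benefit) and incompletely attending families +0.12 to +0.33 SD (false harm). The overall ITT difference stayed within 0.01 of zero. With no correlation, both rows were about zero.

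**Item a.** If two separate splits are meant, the one on baseline diagnosis is sound, and the one on end-of-intervention diagnosis may be affected by treatment. If a diagnosis at both times is meant, the classification still uses information from after randomisation.

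**The case against.** The strongest points on the other side are these.

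- *The bias may be zero.* Under reading 2, if attendance is unrelated to prognosis after baseline adjustment, both rows are unbiased. This is true, but the SAP neither states nor supports that assumption, and it would not make the rows randomised contrasts. It also does nothing for the row that cannot be estimated under reading 1.
- *The lack of TAU access is inferred.* This is also true. If some TAU families had access, the split would still be made after randomisation and would mean different things in the two arms.
- *The figures have no anchor in the SAP.* Agreed. The two sets of assumptions give different ranges, and the illustration leaves out age, sex and the family random effect. The defect is structural and does not depend on the figures.
- *The mismatch with demographic or clinical subgroups is a weak argument.* Item e, on motivation to participate, arguably does not fit that description either. The objection to item d rests on timing and on its being specific to one arm.
- *Removal is not the only remedy.* A complier-type estimand, with its assumptions stated, could address a related question. The SAP names none.
- *It is exploratory.* This stands and limits the consequence: item d is one of five subgroup items.

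**Conclusion.** The point holds. Followed as written, item d produces either a row with no control families, two rows that each compare a self-selected part of VIA with all of TAU, or a within-arm comparison that is not a treatment difference. This conclusion rests on the SAP's own text and on one inference, that TAU families did not attend VIA Family sessions.

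Neither the size nor the sign of any bias can be obtained from the SAP. Under the assumed inputs the false gap between rows in reading 2 is 0.16 to 0.18 SD at k = 0.1 and 0.32 to 0.35 SD at k = 0.2. Its direction depends on whether better-resourced or more burdened families attend in full. The item should be corrected, but the primary ITT analysis is not affected. The timing of diagnosis in item a is a lesser matter that depends on how its wording is meant.

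**What to change.** Remove item d from the subgroups for which a VIA-versus-TAU difference is estimated, and from the forest plot. If the question is wanted, add a descriptive comparison of SDQ change by full-family attendance within the VIA arm, labelled as non-randomised. For item a, state that the treatment difference is estimated by ASD/ADHD diagnosis at baseline.

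The cost is a change of SAP wording, with no new data. The forest plot loses one item, and the within-VIA description cannot show whether full attendance causes a larger effect.
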